### **5.1b Baseline data collection**

All baseline data will be collected after informed consent to participate in the study has been obtained prior to the first physiotherapy session. Participants will be asked to complete a questionnaire at baseline to capture the demographic information and PROMs outlined in section 5.1a. Telephone or email contact will be used to obtain a score, where relevant, if baseline data collection is subsequently identified as being incomplete.

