#### **4.4b Secondary outcomes**

- Acceptability of outcome data collection by participants defined as the % completion of the PROMs outlined below.
- The Tegner Activity Scale measures activity on a scale from 0-10, with higher scores indicating higher activity. It has shown good reliability and content validity in patients with acute patellar dislocation and prior dislocation/subluxation and shown to measure a distinct aspect of recovery demonstrated by its low correlation with knee specific and general health questionnaires in this cohort. It has previously been used to assess the effect of conservative management in patients with first

time LPD patients. It will be completed after informed consent has been obtained prior to the first physiotherapy session based on **pre-injury** activity levels and at 3 months after the first physiotherapy session based on their activity levels at that time. It will be administered as a patient completed questionnaire. The change in Tegner Activity Scale scores will be used for analysis.

[figure not shown]
- The Lysholm Knee Scoring Scale was originally developed for patients with knee ligament injuries and subsequently revised. It is scored from 0-100 with lower scores indicating higher pain and disability. It has since demonstrated good test-retest reliability in patients with first time LPD and prior subluxation/dislocation and was able to discriminate between those who subsequently developed recurrent instability and those who did not. It has been used to assess the effect of conservative management in patients with first time LPD and recurrent LPD. It will be completed after informed consent has been obtained prior to the first physiotherapy session and 3 months after the first physiotherapy session based on **current** knee symptoms at that time. It will be administered as a patient completed questionnaire. The change in Lysholm Knee scores will be used for analysis.
- The EQ-5D is a commonly used quality of life questionnaire. It will be completed after informed consent has been obtained prior to the first physiotherapy session and 3 months after the first physiotherapy session based on **current** symptoms at that time. It will be administered as a patient completed questionnaire. The change in EQ-5D scores will be used for analysis.

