## **SECTION 4.7 Recruitment**

### **4.7a Screening and eligibility assessment**

Clinic lists for the trauma and orthopaedic NPC will be screened for patients with a knee injury. Patients will be assessed by a member of the trauma and orthopaedic team as per their usual practice. Patients subsequently diagnosed with a LPD will be assessed to see if they meet the study eligibility criteria (as described in section 4.2a). Eligible participants will be provided with the participation information sheet and asked if they wish to participate in the study.

Referrals to the trauma outpatient physiotherapy department at the John Radcliffe hospital will also be screened to identify additional potential participants (e.g. patients referred to physiotherapy directly from the Emergency Department (ED) and not seen in the trauma and orthopaedic NPC). Information packs, containing an invitation letter and participation information sheet, will be sent to potential participants with *CF*'s email address and phone number. The invitation letter and participant information sheet will advise that consent to participate in the study is strictly voluntary, ongoing and can be withdrawn at any time (as described in section 7.3). Patients interested in participating in the study will register their interest by telephone or email. An initial consultation to review eligibility criteria and obtain informed consent will be arranged at the time of their first physiotherapy appointment to limit participant inconvenience.

Eligible patients who decline to participate will have their age and gender recorded. They will also be asked their reasons for declining to participate, and if given, these will also be recorded. This will allow us to compare the characteristics of those recruited and those who chose not to participate. Those who do not meet the eligibility criteria or who decline to participate will be referred to their local physiotherapy provider (including the John Radcliffe trauma outpatient department where appropriate) as they normally would.

Informed consent for eligible participants who wish to participate in the study will be obtained as outlined in section 7.3.

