### **SECTION 7.3 Consent**

Written consent will be obtained in accordance with GCP guidelines and by a researcher identified in the delegation log as being able to take consent. Participants will be informed about the study design, aims of the study and what it will involve for them. Participants will be informed the purpose of the study is not to assess the efficacy of the intervention. Participants will also be provided with written information in the form of a participant information sheet and offered an opportunity to ask questions. Participants will be offered time to consider their participation in the study should they wish to do. Participants will be informed their participation is voluntary and ongoing, and they can withdraw consent at any time with no obligation to explain why and without affecting the quality of their care.

If participants are happy to proceed to enrolment in the study the consent form will be signed and dated by the participant and the researcher. A copy will be provided to the patient, a copy will be placed in the patient's medical notes, and the original kept by the study team.

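### Section 5.1b allows missing Lysholm and EQ-5D-5L baseline items to be collected after treatment has started, with no cut-off, although change from that baseline is to be analysed

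*Combined protocol and SAP*

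**What the plan says.** Section 5.1b sets the timing rule: "All baseline data will be collected after informed consent to participate in the study has been obtained prior to the first physiotherapy session". It then adds an exception: "Telephone or email contact will be used to obtain a score, where relevant, if baseline data collection is subsequently identified as being incomplete". The exception carries no latest date and does not say which items it covers.

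Section 4.4b has Lysholm and EQ-5D answered on symptoms at the time of completion, on this schedule: "It will be completed after informed consent has been obtained prior to the first physiotherapy session and 3 months after the first physiotherapy session". It also commits to a use: "The change in Lysholm Knee scores will be used for analysis", with a matching statement for EQ-5D. Baseline Tegner is different, because it refers to activity before the injury.

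Section 4.7a describes two entry routes.

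- **Physiotherapy referrals:** the initial consultation to check the criteria and "obtain informed consent will be arranged at the time of their first physiotherapy appointment to limit participant inconvenience".
- **New Patient Clinic:** "Eligible participants will be provided with the participation information sheet and asked if they wish to participate in the study". Consent then follows Section 7.3, where "Participants will be offered time to consider their participation in the study should they wish to do". Neither section gives the day of consent or of the baseline questionnaire for these patients.

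Section 5.1c counts the 3-month follow-up from the first physiotherapy session. It allows completion at a final appointment that falls within 1 week of that time.

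**The concern.** A baseline symptom score should describe the patient before treatment. The two rules in Section 5.1b conflict whenever a blank is found after session 1, because the item can then no longer be collected at the time the section requires. The exception lets it be collected anyway and entered as baseline.

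A patient asked by telephone some weeks into the programme about current pain, swelling or instability reports a partly treated knee. If the knee is recovering, that baseline is too favourable and the change too small. The patient could be asked to recall the state before session 1, but the plan does not say so, and recall would be a different measurement.

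Two things are at stake. The Lysholm and EQ-5D change scores would mix participants whose changes cover different periods. Filling blanks later could also hide the item-level missingness that Section 5.3b wants reported to help choose instruments for a later study.

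**Working it through.** The plan gives no figure to reproduce on this point. The check is a comparison of the timing rules, followed by date arithmetic.

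**1. Can a late item precede session 1?** On the referral route, Section 4.7a places consent at the first physiotherapy appointment, and Section 5.1b places baseline after consent and before the session. All three therefore fall at one visit. A blank found on the spot can be completed on paper. A blank that needs a telephone call or email has in practice been found after the visit, so after session 1. This step needs no assumption about waiting times.

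**2. Length of the change period.**

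- Input from Section 5.1c: follow-up at 3 months after session 1, plus or minus 1 week where it coincides with the final appointment.
- 3 months = 3 × 365.25 / 12 / 7 = 13.04 weeks, taken as 13.
- Span = 13 − L, where L is the number of weeks after session 1 at which the item is answered. The documents do not give L; 1 to 4 weeks is assumed.

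| L (assumed) | Span | Shortening |
|---|---|---|
| 0 | 13 weeks | none |
| 1 | 12 weeks | 1/13 = 8% |
| 2 | 11 weeks | 2/13 = 15% |
| 4 | 9 weeks | 4/13 = 31% |

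Each span is plus or minus 1 week for the follow-up tolerance.

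**3. Illustrative effect on the mean Lysholm change.** Suppose k of the 15 target participants have a score obtained L weeks late while Lysholm rises r points per week. The mean change falls by k × L × r / 15. All three inputs are assumed: k from 1 to 3, L from 1 to 4, r from 1 to 3.

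- Smallest: 1 × 1 × 1 / 15 = 0.07 points.
- Middle: 2 × 2 × 2 / 15 = 0.53 points.
- Largest: 3 × 4 × 3 / 15 = 2.4 points on the 0 to 100 scale.

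This treats the whole score as late. A single late item would move it less.

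**4. Clinic route.** Baseline must precede session 1, but no maximum gap is stated. With a gap of g weeks the span is 13 + g. The documents do not give g. Values of 0, 2, 4 and 6 weeks (assumed) give 13, 15, 17 and 19 weeks. Zero is fully compatible with the text.

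**5. Can the span be recovered afterwards?** Consent forms are dated (Section 7.3), and the time from injury to session 1 is recorded (Section 5.1a). A baseline completed on schedule therefore lies between known dates. An item obtained later does not, because no questionnaire or item completion date is listed.

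**The case against.** The strongest reply is that little depends on these scores. The secondary outcome served by the questionnaires is percentage completion. Section 4.3b says efficacy is not in question, and Section 5.3a plans only descriptive summaries of the baseline and 3-month scores in one group. No objective asks for an effect estimate or a standard deviation for a later trial. This stands, and it limits the severity. It does not remove the point, because Section 4.4b still says the changes will be analysed, and a contaminated baseline also affects the baseline summary itself.

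A second reply is that the exception in Section 5.1b is qualified by relevance, a qualifier missing from the parallel follow-up rule in Section 5.1c. It could be meant to exclude symptom items. The text does not say so, and by referring to obtaining a score it points towards the questionnaires.

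A reader might infer something stronger: that baseline is not tied to the start of treatment, and that clinic patients complete it weeks before session 1. The documents do not support this. Baseline must precede session 1 and follow-up is counted from it. The text does not say when clinic patients consent or answer, and the timeline schematic in Section 4.5, which may settle it, is not shown in the available text. Any wait of several weeks is an assumption. What remains is that the text states no maximum gap.

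**Conclusion.** The point holds for late completion. Section 5.1b contains a stated rule that, on the referral route, would in practice place post-treatment answers in the baseline of two current-symptom measures. If items are answered 1 to 4 weeks late, the change spans about 12 to 9 weeks instead of 13. The illustrative shift in the mean Lysholm change is about 0.07 to 2.4 points. Those figures rest on assumed delays, numbers of late scores and recovery rates, and the direction assumes that patients are improving.

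For the clinic route the conclusion is weaker: spans may differ because no maximum gap is given, and by how much cannot be determined.

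The consequence is limited to descriptive secondary summaries. The feasibility outcomes on eligibility, recruitment, attrition and adherence are untouched. It should be corrected because the correction is nearly free, but it is no obstacle to running the study.

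**What to change.** Amend Section 5.1b as follows.

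- Check the Lysholm and EQ-5D-5L for blanks before session 1 starts, and complete them then.
- Do not use any current-symptom item obtained after session 1 starts as a baseline value or in a change score. Report it as missing at baseline, consistent with Section 5.3b.
- Keep later telephone or email completion for demographics and pre-injury Tegner, which do not ask about current symptoms.
- Record the date each questionnaire is completed, and report the interval from baseline to session 1.

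Moving every questionnaire to the day of session 1 is not needed. Patients who complete the questionnaires at an earlier consent visit keep that baseline, so people who consent and never attend are not lost from the completion data. The recorded dates show how far the spans differ.

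The cost is a few lines of protocol text, one date field and a brief check at the first visit. The downside is that a few baseline items stay missing, which matters somewhat with a target of 15, although that missingness is itself information the study intends to report.

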### **5.1c Follow up data collection**

Follow up data collection will take place 3 months after the first physiotherapy session. For participants whose final physiotherapy appointment is within 1 week of this time, questionnaires will be administered after this appointment. Follow-up data collection for all other participants will be via postal questionnaire.

At least one reminder, via telephone or email, will be sent to participants who do not return postal questionnaires. Telephone or email contact will be used to obtain a score if follow up data collection is subsequently identified as being incomplete.

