### **SECTION 4.3 Intervention**

All participants will receive the study intervention in addition to standard management of acute LPD by the trauma and orthopaedic service at the John Radcliffe hospital. Typically, this involves the provision of a lateral buttress splint and referral to physiotherapy with no limitations on weight-bearing or knee range of movement. Patients may receive advice on pain management, gait re-training and instruction of basic knee exercise from a member of the orthopaedic team or physiotherapist working in the NPC. No attempt will be made to modify this but what has been delivered in addition to the study intervention will be recorded in the study treatment logs to help characterise what acute care was delivered overall.

The intervention will be comprised of up to 6, one-to-one, physiotherapy sessions over a maximum duration of 3 months. 1 or 2 more sessions will be allowed only if deemed clinically essential. Additional sessions and the reasons for these will be recorded to understand if the intervention would need adapting for future studies. Less than 6 physiotherapy sessions can be agreed with the participant if they are self-managing effectively and their goals have been achieved, (these stopping rules will be recorded). A treatment duration of up to 3 months is representative of current care in the NHS for first-time LPD. Initial physiotherapy sessions will be 45-60 minutes and subsequent physiotherapy sessions will be 30 minutes as per local practice.

The exercise intervention has been designed to address the biomechanics associated with the LPD mechanism of injury, improve common lower limb strength deficits in this patient population and facilitate a return to the participant's desired activities which may include activities such as running, hopping and twisting.

The LPD mechanism of injury is thought to result from a quadriceps contraction with the knee in a position of slight knee flexion, femoral internal rotation and tibial external rotation which forces the patella laterally. This is supported by studies demonstrating peak lateral displacement of the patella at angles of 0-30° knee flexion in patients with patellofemoral

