General health status	EQ-5D-5L	Baseline, 3 months post first physiotherapy session
Intervention delivery	Duration from LPD to first physio session, initial injury management, number of physiotherapy sessions attended, number of physiotherapy appointments participants unable to attend/did not attend, duration of the intervention from enrolment to discharge, exercises and dose of exercise	Completion of intervention

	prescribed from treatment logs completed by therapists	
Harms	Patient and staff reported adverse events including any recurrent patellar dislocation, subsequent listing for knee surgery for mechanical instability and any increases in pain or swelling resulting from the exercise intervention lasting > 1 week	From beginning of intervention to 3 months post first physiotherapy session

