### **SECTION 6.2 Harms**

#### **6.2a Adverse events**

For this study an adverse event (AE) will be described as any unfavourable sign or symptom related to completing the study intervention.

This study involves rehabilitation after a recent LPD. No additional risks are foreseen compared to usual rehabilitation at the John Radcliffe Trauma Outpatient Physiotherapy department.

Possible (expected) complications of rehabilitation are:

Newly acquired or temporary increases in knee pain and knee swelling; delayed onset muscle soreness, persistent patellar instability and recurrent patellar dislocation. Some of these may require the need for further surgery.

Symptoms such as delayed onset muscle soreness and increases in knee pain or swelling lasting less than 1 week that do not require medical attention will not be regarded as AEs, as these are common after commencing a new exercise regime post injury. These will be managed as outlined in section 4.3a and explained in the participation information booklet. In the unlikely event of a further patellar dislocation patients will be referred to the trauma and orthopaedic service for assessment and treatment. If physiotherapist become aware of any AEs while administering the intervention, whether the AE is related to the intervention will be determined by the physiotherapist and verified by *CF* in discussion with his supervisors. All AEs will be recorded on case report forms by the participant's physiotherapist.

AEs related to the intervention will also be recorded by participant reported questionnaire at 3 month follow-up.

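### Participants whose last session falls within 1 week of 3 months can complete the harms record that same day, too soon for a late flare to meet the more-than-1-week criterion, and no later harms contact is described

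*Combined protocol and SAP*

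**What the plan says.** Section 4.3 describes the intervention as "up to 6, one-to-one, physiotherapy sessions over a maximum duration of 3 months", so the last session may fall at or close to the 3-month point. Section 5.1c then sets two routes for follow-up, which is due 3 months after the first session:

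- **Clinic route:** "For participants whose final physiotherapy appointment is within 1 week of this time, questionnaires will be administered after this appointment".
- **Postal route:** "Follow-up data collection for all other participants will be via postal questionnaire".

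The Harms row of section 5.1a covers patient- and staff-reported adverse events. It includes recurrent dislocation, listing for surgery, and "any increases in pain or swelling resulting from the exercise intervention lasting > 1 week". Its window is "From beginning of intervention to 3 months post first physiotherapy session". Section 4.4b instead closes the window at the 3-month follow-up.

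Section 6.2a gives two sources. Staff reports depend on what is learned during treatment: "If physiotherapist become aware of any AEs while administering the intervention". For participant reports, "AEs related to the intervention will also be recorded by participant reported questionnaire at 3 month follow-up". The same section narrows what counts: "increases in knee pain or swelling lasting less than 1 week that do not require medical attention will not be regarded as AEs".

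**The concern.** On the clinic route, the questionnaire that asks the participant about harms can coincide with the last exposure to supervised treatment. A flare provoked by that session has no duration yet, and one that began earlier in the same week has not lasted long enough to qualify. The physiotherapist will not see the participant again. The telephone and email contact in section 5.1c is for unreturned postal questionnaires and incomplete scores, not for new harms. The SAE procedure in section 6.2b also runs only until the exercise intervention finishes.

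Assessing harms is a secondary objective (section 3.2b), and section 4.4b says harms are recorded to inform future research. Following section 5.1c exactly would under-record late events. It would also make ascertainment depend on when a participant happens to finish: someone whose last session was 8 or more days before the 3-month date can report a qualifying flare from it, while someone who finished a day later cannot.

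**Working it through.** The plan gives no figure for this, so the check is day arithmetic.

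**Inputs**
- Day 0 is the 3-month date, where the section 5.1a harms window closes.
- *s* is the day of the final session relative to day 0.
- *q* is the day the questionnaire is completed. On the clinic route (*s* from −7 to +7, section 5.1c), *q* = *s*, assuming same-day completion. On the postal route, *q* = 0, assuming completion at 3 months.
- A flare qualifies on duration if *q* − onset > 7 days (section 5.1a).

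**Formulas**
- Duration at the questionnaire of a flare starting at the final session: *q* − *s*.
- Latest onset that can already qualify, in whole days: *q* − 8.
- Window days after the questionnaire: the larger of 0 and −*q*.
- Onset days up to day 0 that cannot be recorded as qualifying: 0 − (*q* − 8) = 8 − *q*.

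| *s* | Route | *q* | Duration of last-session flare | Latest qualifying onset | Window days after questionnaire | Onset days not recordable |
|---|---|---|---|---|---|---|
| −28 | postal | 0 | 28 (can qualify) | −8 | 0 | 8 |
| −14 | postal | 0 | 14 (can qualify) | −8 | 0 | 8 |
| −8 | postal | 0 | 8 (can qualify) | −8 | 0 | 8 |
| −7 | clinic | −7 | 0 (cannot) | −15 | 7 | 15 |
| −4 | clinic | −4 | 0 (cannot) | −12 | 4 | 12 |
| 0 | clinic | 0 | 0 (cannot) | −8 | 0 | 8 |
| +4 | clinic | +4 | 0 (cannot) | −4 | 0 | 4 |
| +7 | clinic | +7 | 0 (cannot) | −1 | 0 | 1 |

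Rows with *s* above 0 are included because section 5.1c does not say on which side of the 3-month date the appointment must fall.

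**Reading the table**
- About a week of loss (8 days) appears on the postal route too. It comes from pairing a fixed window with a duration threshold. Section 5.1c adds at most 15 − 8 = 7 days.
- What is particular to the clinic route is where the loss falls: it always includes the last session, whereas the postal rows shown do not lose last-session flares.
- When *s* is below 0, up to 7 days of the section 5.1a window follow the questionnaire with no described means of observation. That also affects events with no duration threshold (recurrent dislocation, listing for surgery) and short flares needing medical attention.
- If section 4.4b is followed and the window closes at the follow-up questionnaire, the unobserved days disappear by definition. The duration problem remains.

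**The case against.** The strongest reply is that this is a small gap in a descriptive secondary outcome. The study has a target of 15 participants, no numerical feasibility targets (section 3.2), and an intervention considered of minimal risk (section 6.1). No decision rule depends on the harms count. That stands, and it limits the severity. It does not close the gap.

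Several stronger readings are tempting, but the documents do not support them:

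- *No flare after a final session can enter the harms outcome.* Postal participants whose last session was at least 8 days before 3 months answer late enough to report one. Section 4.3 allows fewer than 6 sessions, so early finishing is provided for.
- *Every flare must exceed 1 week to count.* Section 6.2a excludes a shorter flare only if it also needs no medical attention. The remaining difficulty is that, after a same-day questionnaire, no described route would record such a flare.
- *A calculable share of harms is lost.* Dividing 15 days by a 91-day window (15/91 = 16.5%) gives a share of calendar time. It becomes a share of harms only if onsets are spread evenly, which nothing in the plan states.
- *Participants who complete the full course have the least complete harms data.* They also have staff contact for longest. Early finishers have none after discharge and rely on a recalled postal answer.
- *The gap falls on the most demanding exercises.* Exercises are individualised and done at home at least three times a week, so demanding work may begin well before the last session.

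It is also fair to say that section 5.1c does not expressly require same-day completion, and that the harms items themselves are not in the documents, so they may ask about symptoms still present. Neither supplies a later contact at which duration could be established.

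**Conclusion.** The point holds for participants given the questionnaire at a final appointment within 1 week of the 3-month date. For them, a pain or swelling increase beginning at that session or in the preceding 7 days cannot be recorded as lasting more than 1 week, and no later harms contact or follow-up of an ongoing flare is described. Where that session precedes the 3-month date, up to 7 days of the section 5.1a window are unobserved for all harms.

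The loss is 15, 8 or 1 onset days for a session 7 days early, on the date, or 7 days late. This rests on same-day completion and whole-day counting. The documents do not say how many participants will take this route, so the range is 0 to 15 of 15. Missed events can only lower the recorded count, but by how much cannot be derived from the documents. Severity is minor to moderate.

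**What to change.** Keep the PROM timing as it is and separate the harms items from it:

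1. In section 5.1c, add one harms-only telephone or email contact for clinic-route participants, at least 8 days after the final session and not before the 3-month date. This is a new use of that contact and needs its own sentence. A flare starting at the final session will then have lasted 8 days if it is still present.
2. In sections 4.4b and 5.1a, give the harms window one definition, ending at the later of 3 months and 8 days after the last session.
3. State that any flare ongoing when harms are recorded is followed up once to establish its duration. This also covers onsets shortly after the last session and the residual week on the postal route.
4. Reconcile the duration wording in sections 5.1a and 6.2a. A flare of exactly 1 week is neither above the one limit nor below the other, and the medical-attention condition appears only in section 6.2a.

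The cost is a wording change, at most 15 short scheduled contacts, a brief follow-up for any ongoing flare, and harms data that close 1 to 2 weeks later for some participants.
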